7. PLANNED ANALYSIS

In general, a set of descriptive statistics to be displayed for continuous variables in the clinical trial report will be as follows:

Non-pharmacokinetic variables:

For End-Of-Text tables, the set of summary statistics is: N, mean, standard deviation (SD), min, median, and max.

Tabulation of frequencies for categorical or categorised data will include all possible categories and display number of observations (subjects) with the percentage relative to the respective treatment sequence / regimen. Percentages will be rounded to one decimal place. The category missing will be displayed if and only if there are actually missing values. Percentages will be based on all subjects in the respective subject set whether they have non-missing values or not.

Pharmacokinetic variables:

The analysis of standard PK parameters will be performed according to (2).

7.1 DEMOGRAPHIC AND OTHER BASELINE CHARACTERISTICS

Only descriptive statistics are planned for this section of the report.

7.2 CONCOMITANT DISEASES AND MEDICATION

Concomitant diseases will be coded according to the most recent version of the Medical Dictionary for Regulatory Activities (MedDRA). Concomitant medication will be coded according to the most recent version of the World Health Organisation – Drug Dictionary.

Only listing is planned for this section of the report.

7.3 TREATMENT COMPLIANCE

Treatment compliance will not be analysed as a specific endpoint. Any deviations from complete intake will be addressed in the RPM and described in the CTR.

7.4 PRIMARY ENDPOINT(S)

The analysis will be performed as defined in the CTP, Sections 7.1, 7.2 and 7.3.1.

7.5 SECONDARY ENDPOINT(S)

The analysis will be performed as defined in the CTP, Sections 7.1, 7.2 and 7.3.2.

7.7 EXTENT OF EXPOSURE

Only listing is planned for this section of the report.

7.8 SAFETY ANALYSIS

The analysis will be performed as defined in the CTP. All safety analyses will be performed on the treated set.

7.8.1 Adverse events

AEs will be coded with the most recent version of MedDRA. The analyses of AEs will be descriptive in nature. All analyses of AEs will be based on the number of subjects with AEs and not on the number of AEs.

For analysis of AE attributes such as duration, severity, etc. multiple AE occurrence data on the CRF, will be collapsed into AE episodes provided that all of the following applies:

- The same MedDRA lowest level term was reported for the occurrences
- The occurrences were time-overlapping or time-adjacent (time-adjacency of 2 occurrences is given if the second occurrence started on the same day or on the day after the end of the first occurrence)
- Treatment did not change between the onset of the occurrences OR treatment changed between the onset of the occurrences, but no deterioration was observed for the later occurrence

For further details on summarization of AE data, please refer (3,4).

The analysis of adverse events will be based on the concept of treatment emergent adverse events. That means that all adverse events occurring between the first drug intake till 3 days after last drug intake will be assigned to the treatments period. During the treatment period, all adverse events occurring after a drug intake till 3 days after the drug intake will be assigned to 'on-treatment' and those occurring after on-treatment period till the next drug intake will be assigned to 'off-treatment'. All adverse events occurring before first drug intake will be assigned to 'screening' and all adverse events occurring after last drug intake + 3 days will be assigned to 'post-treatment' (for listings only).

According to ICH E3 (5), AEs classified as 'other significant' needs to be reported and will include those non-serious and non-significant adverse events with

- (i) 'action taken = discontinuation' or 'action taken = reduced', or
- (ii) marked haematological and other lab abnormalities or lead to significant concomitant

therapy as identified by the Clinical Monitor/Investigator at a Medical Quality Review Meeting.

An overall summary of adverse events will be presented.

The frequency of subjects with adverse events will be summarised by treatment, primary system organ class and preferred term (mention MedDRA levels to be displayed in the tables).

The system organ classes will be sorted by default alphabetically. Preferred terms will be sorted by frequency (within system organ class).

7.8.2 Laboratory data

The analyses of laboratory data will be descriptive in nature by treatment sequence and will be based on BI standards (6).

Clinically relevant findings in laboratory data will be reported as AEs and will be analysed as part of AE analysis.

The last value on-treatment is defined as the last non-missing value observed during ‘on-treatment period’ (See section 7.8.1).

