7.3.4 Safety analyses

Safety will be assessed for the endpoints listed in [Section 5.2.1](#). All treated subjects (that is, all subjects who received at least one dose of trial drug), will be included in the safety analysis. Safety analyses will be descriptive in nature and will be based on BI standards. No hypothesis testing is planned.

The analyses will be done by ‘treatment at onset’.

Treatments will be compared in a descriptive way. Tabulations of frequencies/proportions will be used for the evaluation of categorical (qualitative) data, and tabulations of descriptive statistics will be used to analyse continuous (quantitative) data.

Measurements (such as ECG, vital signs, or laboratory parameters) or AEs will be assigned to treatments (see [Section 4.1](#)) based on the actual treatment at the planned time of the measurement or on the recorded time of AE onset (concept of treatment emergent AEs).

Therefore, measurements planned or AEs recorded prior to first intake of trial medication will be assigned to 'screening', those between first trial medication intake until end of the residual effect period (see [5.2.2.2](#)) will be assigned to the treatment period. Events after the residual effect period but prior to next intake or end of trial examination will be summarized as 'post-treatment', those after the end of trial examination will be assigned to 'post-trial'. These assignments including the corresponding time intervals will be defined in detail in the TSAP.

Adverse events will be coded using the Medical Dictionary for Regulatory Activities. Frequency, severity and causal relationship of AEs will be tabulated by treatment, system organ class and preferred term. SAEs and other significant AEs (according to ICH E3) will be listed separately.

Laboratory data will be compared to their reference ranges. Values outside the reference range as well as values defined as clinically relevant will be highlighted in the listings. Additionally, differences from baseline will be evaluated.

Vital signs or other safety-relevant data observed at screening, baseline, during the course of the trial and at the end-of-trial evaluation will be assessed with regard to possible changes compared to findings before start of treatment.

Relevant ECG findings will be reported as AEs.

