7.8.3 Vital signs

Only descriptive statistics by treatment sequence and planned visit are planned for this section of the report.

Clinically relevant findings in vital signs data will be reported as AEs and will be analysed as part of AE analysis.

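### The protocol promises a tablet-versus-capsule description of laboratory values and vital signs, but the SAP tabulates them by treatment sequence and declares no change

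*SAP*

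**What the plan says.** Protocol 7.3.4 sets the rule for safety data: "Treatments will be compared in a descriptive way". It continues: "Measurements (such as ECG, vital signs, or laboratory parameters) or AEs will be assigned to treatments", and the criterion is "based on the actual treatment at the planned time of the measurement or on the recorded time of AE onset". It leaves the detailed assignments and time intervals to the SAP.

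SAP 7.8.2, on laboratory data: "The analyses of laboratory data will be descriptive in nature by treatment sequence and will be based on BI standards". SAP 7.8.3, on vital signs: "Only descriptive statistics by treatment sequence and planned visit are planned for this section of the report".

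For adverse events, SAP 7.8.1 groups differently: "The frequency of subjects with adverse events will be summarised by treatment, primary system organ class and preferred term".

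SAP section 4 reports no changes to the planned analysis, and the opening of SAP 7.8 says that the safety analysis follows the protocol.

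**The concern.** In a crossover trial of two formulations, the useful safety description is tablet against capsule. The protocol says so and names laboratory and vital-sign data among the measurements to be assigned to treatment. It then hands the detail to the SAP, and there the grouping becomes sequence.

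This is not loose wording for treatment, because the SAP uses treatment for adverse events and sequence for these data a few lines later.

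The laboratory panel includes aPTT and prothrombin time (protocol 5.2.3), and the pilot study put tablet exposure at about 110% of capsule (protocol 1.2). A reader would therefore expect to see these values side by side by formulation. If the tables follow the SAP as written, the report will not contain that summary and nothing will flag its absence.

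**Working it through.** **1. The rules compared**

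| Data | Protocol 7.3.4 | SAP |
|---|---|---|
| Adverse events | By treatment | By treatment (7.8.1) |
| Laboratory | Assigned to actual treatment; treatments compared | By sequence; visit split not stated (7.8.2) |
| Vital signs | Assigned to actual treatment; treatments compared | By sequence and planned visit only (7.8.3) |

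The SAP follows the protocol for adverse events and departs from it in the other two rows.

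**2. What a sequence contains**

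The sequences are T-R-R-T and R-T-T-R (protocol 3.1 and the sequence table in protocol 4.1.4). Each has 2 tablet and 2 capsule periods. A contrast of sequence totals therefore carries no tablet-versus-capsule information.

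**3. Values available**

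The Flow Chart schedules, in each period, safety laboratory tests at admission and 24 h, and vital signs pre-dose, at 2 h and at 24 h. The post-dose planned times are thus 24 h for laboratory tests, and 2 h and 24 h for vital signs. With 80 subjects per sequence, all completing:

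- Values per post-dose time: 2 sequences × 80 subjects × 4 periods = 640.
- Two of each subject's four periods are tablet: 160 × 2 = 320 tablet values, and likewise 320 capsule values.

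**4. Vital signs by sequence and visit**

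- Cells per planned time: 2 sequences × 4 treatment visits = 8.
- Values per cell: 640 divided by 8 cells = 80.
- Tablet cells: T-R-R-T periods 1 and 4, and R-T-T-R periods 2 and 3. The other four are capsule cells.
- Each visit sets 80 tablet values against 80 capsule values, and 80 out of 320 is 25% of each formulation's total. The four contrasts are not combined anywhere.

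**5. Laboratory data**

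SAP 7.8.2 does not mention visits, and the company standard that it cites is not available here. Two cases are therefore conditional.

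- *Tables not split by visit.* Each sequence column would hold 80 × 2 = 160 tablet and 80 × 2 = 160 capsule values together.
- *The one summary that the section defines.* "The last value on-treatment is defined as the last non-missing value observed during" the on-treatment period, and SAP 7.8.1 sets that period per dose: "all adverse events occurring after a drug intake till 3 days after the drug intake will be assigned to" the on-treatment category. The end-of-trial visit falls 5 to 14 days after day 1 of Visit 5, so it lies outside the 3-day window. If the term means the last value over the whole trial, a completer with no missing or unscheduled sample contributes the period-4 24 h value. That gives 80 tablet values (T-R-R-T) and 80 capsule values (R-T-T-R), again 80 out of 320, or 25%. If it means the last value within each window, it gives one value per period, each tied to one formulation, but the stated grouping is still sequence.

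**The case against.** The strongest reply has four parts.

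- **The protocol names no pooled table.** Its specific text on laboratory data asks for reference-range checks and differences from baseline, and its text on vital signs asks for change from before treatment. Only adverse events have an explicit by-treatment tabulation. This is true of the specific paragraphs. But the same section names laboratory and vital-sign measurements in its assignment rule and says that treatments will be compared. Assigning a measurement to a treatment serves little purpose if no summary uses the assignment.
- **The SAP covers the gap elsewhere.** SAP 7.8 defers to the protocol, SAP 6.1.1 defines reference and test intervals, and SAP 7 mentions regimen in a rule on percentages. The deferral only makes the SAP contradict its own subsections, and the specific wording would normally govern programming. The mention of regimen is a general denominator rule. The intervals in SAP 6.1.1 are not used in 7.8.2 or 7.8.3. They could not serve as written either: each washout interval starts one minute after dosing, so the 2 h and 24 h measurements would fall in washout.
- **Formulation can be read from sequence plus visit.** This stands for vital signs, and no information is lost. The comparison is left to the reader, however, in four separate pieces.
- **Little depends on it.** This also stands. No hypothesis test is planned, clinically relevant findings become adverse events and are tabulated by treatment, and both products deliver the same 110 mg dose. It limits the weight of the point but does not remove the inconsistency. Adverse event tables show only findings judged clinically relevant, not the distribution of values.

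**Conclusion.** The concern holds. SAP 7.8.2 and 7.8.3 group laboratory and vital-sign data by sequence, where protocol 7.3.4 assigns them to actual treatment and calls for a treatment comparison. No departure is declared.

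For vital signs, each planned contrast uses 25% of each formulation's values, and the formulation-level summary (320 against 320 per post-dose time) is never stated. These counts assume 160 completers with full data. For laboratory data the layout is unknown: the mixed columns of 160 and 160 assume no visit split, and the 80-against-80 last value assumes the whole-trial reading.

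The consequence is confined to descriptive safety tables. The point should be corrected, but it does not bear on the bioequivalence conclusion.

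**What to change.** - In SAP 7.8.2 and 7.8.3, add descriptive summaries by actual treatment (tablet, capsule) and planned time. Assign each post-dose measurement to the formulation dosed in that period, in line with the 3-day on-treatment window in SAP 7.8.1.
- Keep the sequence tables as supplementary, and state in 7.8.2 whether they are split by visit.
- State in 7.8.2 whether the last on-treatment value is taken per dose or over the whole trial.
- If by-treatment summaries are not intended, declare and justify that in SAP section 4.

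The cost is a few sentences in the SAP and a few extra tables. The measurements are already scheduled in every period, so no new data are needed.

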7.8.3 Vital signs

Only descriptive statistics by treatment sequence and planned visit are planned for this section of the report.

Clinically relevant findings in vital signs data will be reported as AEs and will be analysed as part of AE analysis.

7.8.4 ECG

ECG data will not be listed but clinically relevant abnormal findings will be reported as adverse events.

7.8.5 Others

No other parameter will be analysed.

10. HISTORY TABLE

Table 10: 1 History table

Version	Date (DD-MMM-YY)	Author	Sections changed	Brief description of change
Initial	16-JUN-2017		None	This is the initial TSAP with necessary information for trial conduct.
Final	12-JUL-2017		Section 5, 6 and 7	Details for analysis are specified. For iPv Table 6.1.1: 1, “none or PKS” and “All” was replaced with “PKS” and “TS and PKS” for clarification. iPv categories have not been changed.
